Assessments. Outcome assessments evaluate changes at 1- and 6-months post-intervention, relative to control for these primary outcomes: Do male adolescents report a higher prevalence of condom use at last sex (for those who have debuted) or anticipated risk behaviors (for those who have not debuted) relating to HIV and STI risk acquisition or transmission?; Do male adolescents report fewer experiences of sexual violence perpetration or attempts to perpetrate sexual violence?; and Do male adolescents report increased intentions for active bystander intervention? All measures utilized in the current study are well established, and tested in our prior studies including the complementary *Safe South Africa* trial. We collect self-reported outcome assessments using audio-computer assisted self-interviewing software which limits social desirability bias.⁷⁸ See **Table 2**.

Table 2: Outcome Measures and Satisfaction Assessment					
Outcome	Measures	Baseline	After Intervention	1-month	6-month
Teachers and Adolescent Boys					
Acceptability	Client Satisfaction Questionnaire ⁷⁹		✓		
Teachers					
Teacher intervention for negative adolescent sexual and IPV behaviors	The Perceptions of School Personnel Helping Scale ^{80,81}	✓	✓		
Active Bystander Behaviors	Miller Likelihood to Intervene, Miller Positive and Negative Bystander Behavior ⁸²	✓	✓		
Sexual aggression norms relating to HIV transmission and IPV; endorsement rape myths, traditional gender roles; social norms regarding sex and violence; norms around HIV transmission including condom attitudes, HIV stigma	Illinois Rape Myth Acceptance Scale ⁸³ ; Boeringer's Social Norms Measure ⁸⁴ ; Gender Equitable Mens Scale ⁸⁵ ; AIDS Related Stigma Scale and Internalized AIDS-Related Stigma Scale; Condom Attitudes Scale - Adolescents	✓	✓		
Adolescent Boys					
HIV Risk Behavior & Intentions: HIV and STI status; HIV testing; frequency sex; number and type of partners; use of condoms	• Items taken from South African trials & NIH's Adolescent Medicine Trials Network for HIV/AIDS Interventions	✓		✓	✓
IPV Perpetration Behaviors: type, frequency and severity of IPV; sexual perpetration and aggression, dating violence	• Sexual Experiences Survey Short Form Perpetration ⁸⁶	✓		✓	✓
Bystander Intervention Behaviors: proactive bystander behavior; bystander efficacy and readiness	• Sexual Social Norms Inventory ⁸⁷ • Bystander Behavior Scale ⁸⁸⁻⁹⁰ • Intent to Help Scale ^{88,90} • Bystander Efficacy Scale ^{89,90}	✓		✓	✓

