Analysis and Further Intervention Refinement. We will check all forms for missing data in field and during entry, with at least 2 telephone calls to participants to collect missing data. We will examine key variables for skewness, variability, missing data, and outliers, with transformations to achieve normality if needed. For our acceptability data (satisfaction assessments), we will set 80% reporting positive ratings as a marker of acceptability and examining process data on satisfaction with format, length, etc. For our fidelity data, we will assess fidelity of facilitator implementation, setting 80% as acceptable fidelity, and using data to make final adjustments to training. For our feasibility data, we will also evaluate feasibility in regards to recruitment ease, and retention during outcome timepoints. For trial outcomes, preliminary analyses will include studies of patterns of missing data , dropout rates, and correlations effect size estimates with small samples have large standard errors so we use pilot data to assess hypothesized intervention effects.¹⁰⁴ We will examine key variables for skewness, variability, missing data, and outliers, with transformations to achieve normality if needed. We will examine descriptive statistics for main outcomes and mediators with extreme scores or deviations from normality to be addressed in subsequent analyses. Baseline differences between groups on demographic variables will be examined using t-tests or the Chi-square test, where appropriate, and variables that show differences will be included as covariates in outcome analyses. McNemars test, for paired binary variables, will be used to determine whether the follow-up measurements significantly differ from baseline measurements in the intervention and control arm, separately. Generalized linear mixed (random effects) models, will be used to compare intervention and control group, via treatment by time interaction terms, following intention-to-treat principles. In exploratory analysis, we will look at directions of hypothesized effects. While we are underpowered to test mediation effects directly, we will explore differences between study arms. Effect sizes observed will be used to inform a larger adequately powered RCT. We also examine exposure to other interventions to see how this may be affecting outcomes.

Rigor, Reproducibility, and Transparency

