The primary objective of this pilot is to test the feasibility and acceptability of the intervention and to generate meaningful effect size estimates for a future fully-powered RCT. We considered sample size needed to demonstrate increased condom use at last sex, reduced sexual violence perpetration, and increased active bystander behavioral intentions. To measure significant change in the three objectives, a total of N=282 adolescent boys will be enrolled, with n=141 in the intervention arm and the same number (n=141) in the control arm. The power calculations described below are based on a McNemar's test for paired proportions, 80% power, and type 1 error rate (alpha) of 5%. These calculations were generated by findings of the R34 testing *Safe South Africa* (R34MH113484-01), which included 80 male adolescents aged 15-17 years. **Condom use:** We assume that in the *Schools Championing Safe South Africa* pilot trial, 88% of male adolescent participants will have ever had sex at baseline, and 63% of those will report at baseline that they used a condom at last sex. **Table 5** shows the sample size required to detect changes between baseline and 6-months in condom use ranging from 3% to 17% at six months at 80% power and a type 1 error rate of 5%. For example, Table 5 shows a sample size in excess of 1000 (N=1138) is required to detect changes in condom usage that are less than 5 percent. To detect larger differences, for example 10% or greater, a maximum sample size of 276 participants is required. To detect changes of 15% or greater in condom use at last sex between baseline and 6 months in the intervention arm, assuming 0.20 correlation between paired observations, 135 adolescent boys are required in the intervention arm. To account for a 3% dropout rate (observed in the *Safe South Africa* study), a total of 141 per arm will be enrolled. **Sexual violence perpetration:** We assume that at baseline, 56% of male adolescent participants will have perpetrated sexual violence in the past 6 months. To detect changes 16% or greater in sexual violence perpetration of sexual violence between baseline and 6 months in the intervention arm, assuming a 0.20 correlation between paired observations, a total of 125 adolescent boys are required in the intervention arm (Table 5). The planned sample size of 141 per arm will account for greater than 3% dropout rate. **Active bystander behavior:** We assume at baseline, 60% of male adolescent participants will have intentions to engage in active bystander behavior. To detect changes 15% or greater in active bystander intentions between baseline and 6 months in the intervention arm, assuming 0.20 correlation between paired observations, a total of 125 adolescent boys are required in the intervention arm (Table 5).

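### Bystander intention is measured on scales but sized, and tested within arm, as a yes/no outcome with no cut-point; analysing the score would be more precise at almost no cost

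*Combined protocol and SAP*

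**What the plan says.** Table 2 (Outcome Measures and Satisfaction Assessment) lists four instruments for the boys' bystander domain at baseline, 1 month and 6 months. They are a social norms inventory, a behaviour scale, an efficacy scale and the "Intent to Help Scale". The Assessments paragraph asks whether intentions increase and sets no threshold.

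Sample Size and Power Considerations (in Aim 3 and again under Statistical design and power) treats the outcome as a proportion: "We assume at baseline, 60% of male adolescent participants will have intentions to engage in active bystander behavior". The calculations are "based on a McNemar's test for paired proportions, 80% power, and type 1 error rate (alpha) of 5" per cent. The target is stated as follows: "To detect changes 15% or greater in active bystander intentions between baseline and 6 months in the intervention arm", "assuming 0.20 correlation between paired observations". The requirement given is 125 boys in the intervention arm, and Table 5 shows the same figure for 0.60 to 0.75.

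Analysis and Further Intervention Refinement states that "McNemars test, for paired binary variables, will be used to determine whether the follow-up measurements significantly differ from baseline measurements", separately in each arm. The arms are compared with generalized linear mixed models using treatment-by-time terms. No distribution or link is given for the bystander outcome. Nowhere do the documents give a scoring rule, a cut-point, a mean or an SD for any bystander scale, or say which of the four instruments defines having intentions.

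**The concern.** A graded score is reduced to yes/no for planning and for the only test of change that is explicitly named. Three things are at stake.

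- **Precision.** Cutting a score into two groups discards information about how far each boy moved.
- **Definition.** Without a cut-point or a named instrument, the 60% has no operational meaning, and the threshold could be chosen after the data are seen.
- **Use for the next trial.** The stated objective includes effect-size estimates for a future fully powered trial. A change in a proportion tied to an undefined threshold is a weaker planning input than a mean change with its SD and correlation.

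**Working it through.** **Inputs from the documents.** Baseline p1 = 0.60; 6-month p2 = 0.75; d = 0.15; correlation of paired binary observations 0.20; 80% power; alpha 5% (sidedness is not stated, but two-sided reproduces the table); 141 per arm; 3% dropout, so 141 × 0.97 = 136.8, about 137 completers.

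**Inputs assumed.** The score is normal with constant SD, and the intervention shifts its mean. The documents supply neither.

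**1. Reproduce the plan's figure.**
- p11 = p1·p2 + 0.20·√(p1q1p2q2) = 0.450 + 0.20 × 0.2121 = 0.4924
- Discordant proportion pd = 0.60 + 0.75 − 2 × 0.4924 = 0.3651
- n = [1.960·√pd + 0.842·√(pd − d²)]² / d² = [1.184 + 0.493]² / 0.0225 = 125.0

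This matches the stated 125. The same formula reproduces every bystander row of Table 5.

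**2. Information kept by one 60/40 cut of a normal score.** φ(0.2533)² / (0.60 × 0.40) = 0.3863² / 0.24 = 0.622. About 38% is lost, which alone implies a factor of 1/0.622 = 1.61 in sample size.

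**3. The planned shift on the score.** Φ⁻¹(0.75) − Φ⁻¹(0.60) = 0.6745 − 0.2533 = 0.421 SD.

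**4. Pairs needed for a paired mean change.** n = (1.960 + 0.842)² × 2(1 − r) / 0.421²

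| Score correlation r | Pairs | 125 ÷ unrounded pairs |
|---|---|---|
| 0.20 (same value as the binary correlation) | 70.8, so 71 | 1.77 |
| 0.33 (latent normal correlation giving a binary correlation of 0.20) | 59.1, so 60 | 2.12 |

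These ratios exceed 1.61 for two reasons. At 75% the cut is further off centre and keeps only 53.9% of the information. In the second row, dichotomising has also weakened the baseline-to-follow-up correlation.

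**5. Power at 137 completers, within arm.**
- McNemar: Φ[(√137 × 0.15 − 1.184) / 0.585] = Φ(0.976) = 84%
- Score, r = 0.20: Φ[0.421 × √(137/1.6) − 1.960] = Φ(1.94) = 97%
- Score, r = 0.33: Φ(2.31) = 99%

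At 80% power the score analysis could detect about 0.28 to 0.30 SD, equivalent to moving from 60% to about 70% or 71%.

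**6. Does enrolment depend on this outcome?** No. For condom use, 0.63 to 0.78 needs 119 sexually active boys, and 119/0.88 = 135. The plan states that "135 adolescent boys are required in the intervention arm" and builds 141 per arm on that figure. Condom use at last sex is binary by nature.

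**The case against.** The strongest reply has four parts.

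- **The treatment comparison may already be continuous.** The mixed model's distribution is left open. The same paragraph plans normality checks and transformations, and the predecessor trial's gender-norm and rape-myth scales were reported as scores. This stands in part. A reader might infer that the between-arm analysis is binary, but the documents do not say so; they leave it unspecified. What is explicitly binary is the sizing and, by its own description, McNemar's test. If a score model is intended, it does not match the basis of the power calculation.
- **Nothing in this trial shrinks.** This stands. A reader might infer that enrolment has been inflated or could be halved. It could not, because condom use sets it, and even the binary bystander analysis exceeds its 80% target.
- **The size rests on unseen data.** This stands. No SD, distribution or score correlation is given, skew or a ceiling would change the figures, and nothing shows that the 60% came from cutting the Intent to Help Scale. That the scale has several items is inferred from its name. The missing cut-point and unnamed instrument do not depend on these assumptions.
- **The gain is for an uncontrolled within-arm change.** This stands. With one school per arm, the between-arm contrast is confounded with school however finely the outcome is scored.

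**Conclusion.** The point holds as a cheap improvement, limited to the bystander outcome. A scale-measured intention is sized as a proportion, McNemar's test is the named test of within-arm change, and neither the measure nor the cut-point is fixed.

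Under a normal score with a pure mean shift, the yes/no form needs about 1.8 to 2.1 times as many pairs for the within-arm test (125 against 60 to 71). Equivalently, power is 84% rather than about 97% to 99% at 137 completers. It is tempting to read the 38% information loss as itself a doubling of the sample. It is not: that loss alone gives about 1.6, and the larger ratios belong to the specific paired comparison. An unpaired two-arm comparison of the same shift, ignoring clustering, gives about 1.7 (152 against 89 per arm).

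The consequence is a less precise and less reusable estimate for one outcome of a pilot whose main objective is feasibility and acceptability. The trial's size is unaffected.

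**What to change.** In Assessments and in Analysis and Further Intervention Refinement:

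1. Name one bystander measure in advance, for example the Intent to Help Scale score, with its scoring rule.
2. Analyse it as a score in the mixed model with treatment-by-time, stating the distribution and link.
3. For this outcome, replace McNemar's test with the paired mean change and 95% CI in each arm. Report the SD and the baseline-to-follow-up correlation for planning the next trial.
4. Keep any yes/no version as a secondary summary, with a cut-point fixed before the data are seen.

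The cost is wording only. The scales are already collected at all three time points, and the binary sample-size figures can stay as a conservative reference. There are two downsides. The score may be skewed or have a ceiling, so the plan should include a distribution check and a robust or bootstrap CI. A mean change is also slightly harder to interpret than a percentage, which the secondary summary in item 4 covers.

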We propose a multiple PI leadership plan that involves sharing responsibility by two M-PIs, [name] (Brown University) and [name] (South African Medical Research Council). This scientific collaboration is stronger than a study conducted by either the USA-based or South African-based team alone. We are able to consolidate expertise with South African adolescents at risk for HIV and IPV. This collaboration also illustrates our philosophy of multidisciplinary and equitable international research partnerships. [name] contributes significant expertise in behavioral and social risk. She also brings expertise in mixed-methods for intervention development and adaptation of empirically supported programs to the South African context as well as international data systems and mobile data collection in South African community contexts. Her experience will facilitate tracking and tracing of adolescents for collection of data in the community setting, and high quality data collection from adolescents on sensitive topics. [name] contributes significant experience in school-based interventions including interventions that focus on the endpoint of adolescent health including adolescent HIV, sexual and reproductive health, and IPV. She brings vast expertise in intervention trial design, implementation, analyses, and dissemination for maximum health systems and policy impact.

[name] will have oversight of Brown University activities including the subcontract to the University of Cape and submission of reports to NIH. This includes annual research performance progress reports, reporting for NIMH's recruitment milestones system, clinical trials registry reporting, and Brown University reporting. [name] will have oversight over the South African Medical Research Council subcontract activities, in close collaboration with [name]. [name] will oversee coordination of stakeholder meetings in South Africa, as well as seeking permission to work with the South African Department of Education. [name] will oversee the day to day management of the South African team, given the time difference between countries. However, [name] will coordinate all weekly team meetings. Together, [name] and [name] will oversee project progress summarized weekly in order coordinate scientific, fiscal and administrative management of the project, setting priorities for allocation of resources and funds; [name] will focus on summarizing the activities

occurring on the USA side (reporting, data systems, data analysis) and [name] will focus on summarizing the activities occurring on the South African side (field-based primary data collection). Together, Drs. [name] and [name] will ensure adequate systems, working with their experienced institutional financial and grants management teams, to ensure that grant activities are in compliance with US laws, and DHHS and NIH policies, including biosafety, the protection of Human Subjects, data and facilities, as well as parallel applicable laws and policies in South Africa. In the case of unanticipated serious adverse events, and with the permission of children and parents, we will refer to services by tapping into the extensive social service and clinical networks that we have worked with for adolescent health in South Africa including both Drs. [name] and [name] respective affiliation with the Medical School at University of Cape Town with [name] taking specific charge of the immediate response needed given the time difference.

Authorship for peer-reviewed manuscripts, book-chapters, scientific conference presentations, policy and clinical briefs, and dissemination briefs resulting from project activities will be determined prior to creating drafts for these outputs. Authorship will be negotiated based on the relative scientific contributions of the PIs, Co-I, consultant, and key personnel, following international guidelines set by the International Committee of Medical Journal Editors (ICMJE). All decisions regarding the technical aspects of the project will be decided jointly in weekly Skype meetings by the M-PIs and Co-Is. In the unlikely case of conflicting opinions regarding the technical approach of the study, the M-PIs, Drs. [name] and [name] will consult with co-I and consultants (Drs. [name], [name], and [name]).

References

1. UNAIDS. Global AIDS Response: Country Progress Report 2012, Republic of South Africa. Pretoria: Republic of South Africa; 2012.
3. Jewkes R, [name] Y, Dunkle K, Morrell R. Relationship between single and multiple perpetrator rape perpetration in South Africa: A comparison of risk factors in a population-based sample. *BMC Public Health* 2015;15:1-10.
